2 STUDY OBJECTIVES

2.1 Primary Objective(s)

The primary objective of the study is to assess the patient level CDR and region level PPV of rhPSMA-7.3 (¹⁸F) PET for BCR of PCa using histopathology or imaging as a SoT. The CDR is defined as the percentage of all patients scanned who have at least one TP lesion (localized correspondence between rhPSMA-7.3 (¹⁸F) PET imaging and the reference standard) regardless of any coexisting FP findings. When determining the region level PPV, all rhPSMA-7.3 (¹⁸F) PET-positive regions will be categorized as TP or FP regions using histopathology or imaging.

2.2 Secondary Objective(s)

The secondary objectives of the study are to:

1. Assess the patient level CDR and region level PPV of rhPSMA-7.3 (¹⁸F) PET in the subgroup of patients who have negative baseline conventional imaging (classified at the site level).
2. Assess the patient level CDR and region level PPV of rhPSMA-7.3 (¹⁸F) PET separated into subgroups of patients with reference standard histopathology available and unavailable.
3. Assess the patient level CDR and region level PPV of rhPSMA-7.3 (¹⁸F) PET stratified by PSA level.
4. Assess the CDR of rhPSMA-7.3 (¹⁸F) PET on a region level.
5. Assess the impact of rhPSMA-7.3 (¹⁸F) results on the intended clinical management of study participants using a clinician survey.
6. Assess the inter- and intra-reader agreement of rhPSMA-7.3 (¹⁸F) scan interpretation by the blinded independent readers.
7. Assess the safety of rhPSMA-7.3 (¹⁸F) injection in patients.

Parexel International

Blue Earth Diagnostics Ltd
BED-PSMA-302

Statistical Analysis Plan

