3.2.2.1 Step 2: Historical and Baseline Conventional Imaging SoT

If historical conventional images (as defined in CSP Section 9.1.5.2) had been acquired prior to acquisition of the baseline conventional images as part of the patient's PCa management, then these images can be used along with baseline to establish the SoT.

Parexel International

Blue Earth Diagnostics Ltd
BED-PSMA-302

Statistical Analysis Plan

Where historical conventional images (e.g. Computed tomography [CT], Magnetic resonance imaging [MRI], bone scan, PET) are available that could be relevant to confirmation of an identified rhPSMA-7.3 (¹⁸F) PET-positive lesion then as many prior imaging series as practical (from approximately the last 2 years) should be made available to the central reviewers.

In cases where historical imaging and baseline conventional images are deemed sufficient (by local site reader) for SoT determination, then this will be acceptable, and follow-up confirmatory imaging (Steps 3 and 4) will not be needed.

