3.2.2.2 Step 3: Confirmatory Imaging SoT (up to 45 Days Post-rhPSMA-7.3 (¹⁸F) PET)

In cases where, in the opinion of the local site reader, historical conventional images are not available or are inconclusive in comparison to baseline imaging, rhPSMA-7.3 (¹⁸F) directed (for confirmation of lesion location only) follow-up confirmatory imaging of the site(s), will be acquired. Confirmatory imaging will be acquired at the discretion of the local investigator(s), with reference to the Technical Operations Manual.

3.2.2.3 Step 4: Additional Confirmatory Imaging SoT (up to 90 Days Post-rhPSMA-7.3 (¹⁸F) PET)

If in the opinion of the local investigator(s) the above imaging Steps 2 or 3 do not allow SoT verification, then a final follow-up, rhPSMA-7.3 (¹⁸F) PET directed (for confirmation of lesion location only) confirmatory imaging scan can be obtained up to 90 days post rhPSMA-7.3 (¹⁸F) PET.

Reading of conventional and confirmatory imaging to determine the next steps in the confirmation process will be performed locally.

Both the rhPSMA-7.3 (¹⁸F) PET scans and all available conventional (historical and baseline) and confirmatory imaging scans acquired under Steps 2 to 4 above will be read centrally for the primary endpoint assessment, according to [Table 1](#) and [Figure 1](#) below. Reads of the conventional and confirmatory imaging as SoT will be directed by rhPSMA-7.3 (¹⁸F) PET findings (for confirmation of lesion location only) and performed by different readers than the blinded, independent rhPSMA-7.3 (¹⁸F) interpretations. Three central reviewers will review all submitted images and reach consensus on the nature of the PET positive target lesion(s). A brief summary of clinical information will be made available to the readers (e.g. 67-year-old male post-RP with pelvic lymph node dissection (PLND) and adjuvant pelvic RT 5 years before; PSA rising to 1.2 ng/mL prior to rhPSMA-7.3 (¹⁸F) scan; PSA_{Adt} 9 months). Readers will be blinded to all other information. Further details are given in the study Independent Review Charter.

rhPSMA-7.3 (¹⁸F) positive lesions will be categorized by the consensus central SoT read as positive, negative or indeterminate using all available conventional and confirmatory imaging. Indeterminate classifications will be categorized as False Positives for the primary analysis. Further details are given in the study Independent Review Charter.

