If a positive lesion on rhPSMA-7.3 (¹⁸F) PET is confirmed by SoT, the lesion will be considered TP. For the primary efficacy analysis, a region will be categorized as a TP if at least one rhPSMA-7.3 (¹⁸F) PET positive lesion is confirmed in that body region (prostate bed, pelvic lymph nodes or other [bone, extra-pelvic lymph nodes and soft tissues/parenchyma] sites), regardless of any coexisting FP lesions in that region. For the primary analysis, pelvic lymph nodes will include the right and left external iliac, obturator, hypogastric (internal iliac), perirectal and presacral lymph node groups.

Parexel International

Blue Earth Diagnostics Ltd

BED-PSMA-302

Statistical Analysis Plan

If all above SoT techniques fail to positively confirm the PET-positive lesion(s), the rhPSMA-7.3 (¹⁸F) PET lesion will be deemed FP.

Table 1: Central Reading Plan

[figure not shown]
Imaging	Modalities	Image Interpretation	# Readers	Read Criteria
rhPSMA-7.3 (¹⁸ F)	rhPSMA-7.3 (¹⁸ F) PET	Blinded, independent, central reads	3	Further details are given in the Study Independent Review Charter
Conventional (Baseline and Historical) and Confirmatory Imaging as SoT	Conventional: Pelvic CT or MRI, bone scan, chest CT, Axumin. Confirmatory: Examples include: specific body region MRI (including functional or multi-parametric MRI), CT, Axumin, NaF PET, etc.	rhPSMA-7.3 (¹⁸ F) directed, consensus image reads. A brief summary of clinical information will be available to the readers (e.g. 67 year old male post-RP with PLND and adjuvant pelvic RT 5 years before; PSA rising to 1.2 ng/mL prior to rhPSMA scan; PSAdt 9 months). Readers will be blinded to all other information.	3 via consensus	Longitudinal assessment of all available conventional and confirmatory imaging scans per standard of care / society guidelines. Further details are given in the study Independent Review Charter. Specifically allowing, for example: a) sub-cm changes in LN size on CT during progression/therapy response to be indicative of cancer or b) small bone CT scleroses to be indicative of cancer

CT=computed tomography; ¹⁸F=fluorine-18; LN=lymph node; MRI=magnetic resonance imaging; NaF=sodium fluoride; PET=positron emission tomography; PLND=pelvic lymph node dissection; PSA=prostate-specific antigen; PSAdt=prostate specific antigen doubling time; rhPSMA=radiohybrid prostate-specific membrane antigen; RP=radical prostatectomy; RT=radiation therapy.

Parexel International

Blue Earth Diagnostics Ltd
BED-PSMA-302

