4.15 Standard of Truth

The SoT algorithm is explained in Section 3.2.

The SoT of PET positive lesions identified by local investigator will be listed by subject, region and lesion showing each of the four steps, as applicable, including final assessment (positive/negative/unknown). Lesions for which only part of the SoT steps are performed will be listed including the step(s) which is/are not performed. Lesions for which no SoT is performed will be listed including Step 1 and 2.

The central read of SoT will be listed by subject and will include SoT proven, with reason(s) for justification. In addition, a listing will be provided showing the modality of the reason, combining

Parexel International

Blue Earth Diagnostics Ltd
BED-PSMA-302

Statistical Analysis Plan

local histology and central read consensus reasons. Finally, a listing will be made of lesion size, including detection by blinded PET reader. The central SoT read will be summarized by region.

The SoT of PET positive lesions identified by the blinded independent PET readers will be listed by subject, reader, region and lesion, showing result for either of three steps: Histological SoT (Step 1) or historical and baseline Imaging SoT (Step 2) or confirmatory Imaging SoT (Step 3 and 4). Any PET positive lesion deemed not a TP according to the SoT will be declared a FP.

The SoT at a region level will be listed by subject, blinded PET reader and region, including SoT result. Regions where no lesion(s) were identified will not be listed. PET positive regions where no SoT positive lesions are present will be FP. PET positive regions with one or more SoT positive lesion(s) will be TP. PET negative regions with one or more SoT positive regions will be FN.

The SoT at a region level will be summarized by blinded PET reader and region using the EAP. The summary will include the number of subjects with positive lesions per region, the number of TP, FP patients per region, the PPV for the regions, including 95% two-sided CIs using the clustered binary data algorithm (Section 4.16.1.3).

Patient level SoT will be listed by subject, blinded PET reader, including result. Patients where no positive lesion(s) were identified by both PET and SoT will not be listed.

Patient level SoT will be summarized by blinded PET reader using the EAP. The summary will include the CDR, including two-sided exact 95% CIs.

An additional summary will show at which step the SoT was determined by the local investigator.

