4.16.3 Secondary Efficacy Variables

4.16.3.1 Patient level CDR and region level PPV of rhPSMA-7.3 (^{18}F) PET in the subgroup of patients who have negative baseline conventional imaging.

This will be a repeat of the primary efficacy using patients from the EAP with negative baseline conventional imaging (according to site reads). The point estimates and two-sided 95% CIs of CDR and PPV will be displayed for each of the blinded independent readers and their majority.

4.16.3.2 Patient level CDR and region level PPV of rhPSMA-7.3 (^{18}F) PET for recurrence in those patients with and without reference standard histopathology available.

For CDR, this will be repeats of the primary efficacy using patients from the EAP and one more condition:

1. Patients with standard histopathology for SoT assessment
2. Patients with no standard histopathology for SoT assessment

For PPV, this will be repeats of the primary efficacy using patients from the EAP and one more condition:

1. Regions with standard histopathology assessment
2. Regions with no standard histopathology assessment

The point estimates and two-sided 95% CIs of CDR and PPV will be displayed for each set of patients for each of the blinded independent readers and their majority.

4.16.3.3 Patient level CDR and region level PPV of rhPSMA-7.3 (^{18}F) PET stratified by PSA level.

This will be repeats of the primary efficacy using patients from the EAP. The last PSA level before the PET scan will be used to stratify the patients (see Section 4.10 for categories). The point estimates

Parexel International

Blue Earth Diagnostics Ltd

BED-PSMA-302

Statistical Analysis Plan

and two-sided 95% CI of CDR and PPV will be displayed for each set of patients for each of the blinded independent readers and their majority.

4.16.3.4 CDR of rhPSMA-7.3 (¹⁸F) PET in the following regions: local recurrence, pelvic lymph nodes, other.

This analysis will use the EAP. The analysis will be performed for each region and for each of the blinded independent readers and their majority. The frequency of confirmed detection will be summarized, including proportion and exact CI of the proportion.

4.16.3.5 Percentage of patients in whom rhPSMA-7.3 (¹⁸F) PET imaging results changed the intended patient management (major and other changes).

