4.16.4 Exploratory Efficacy Variables

4.16.4.1 The overall patient level detection rate (without SoT confirmation), including detection rate subgroup analyses of patients: a) who have negative baseline conventional imaging (according to site read), b) with reference standard histopathology available and unavailable, and detection rate stratified by PSA level and assessed by region.

This concerns several similar analyses. In each analysis the frequency of patients with a PET positive lesion will be counted, proportion of positive patients including exact CI will be provided. Each analysis will be performed for each of the blinded independent readers and their majority.

- patients in the FSP who have PET scan and who have negative (no lesions detected at all) baseline conventional imaging.
- patients in the FSP who have PET scan and have reference standard histopathology.
- patients in the FSP who have PET scan and do not have reference standard histopathology.
- For each region (local recurrence, pelvic lymph nodes, other) patients in the FSP who have PET scan using subgroups by PSA levels (Section 4.10).

4.16.4.2 Patient level PPV in which a TP patient is defined as having at least one TP region, regardless of any coexisting FP regions.

This concerns all patients in the EAP. The patient level PPV frequency and proportion, including exact CIs will be provided for each of the blinded readers and their majority.

4.16.4.3 The number of positive rhPSMA-7.3 (¹⁸F) scans compared to conventional imaging in defined regions, leading to upstaging of the patient a) post-RP; b) post--RT.

This concerns patients with negative baseline scan in subgroups of the EAP with an extra subgroup condition, for a) the patient has had RP (with or without RT), for b) the patient has had RT (without RP) or c) patient has other therapies. (For definitions of RT and RP, see Section 4.8). The patients will be counted if they have any TP lesion in either of the regions (local recurrence, pelvic lymph nodes, other) for each of the blinded readers and their majority.

4.16.4.4 Patient and regional level detection rates of rhPSMA-7.3 (¹⁸F) PET.

This concerns the subgroup of patients in the FSP who have a PET scan. The regions analysis will concern local recurrence, pelvic lymph nodes and other. The frequency of detection, detection rate including exact CI will be determined for each of the blinded readers and their majority.

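### Results in conventional-imaging-negative men mix in True Positives whose proof may include the baseline scans the site called negative, and the plan does not separate them

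*SAP*

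**What the plan says.** **Entry to the subgroup.** Secondary objective 1 (SAP 2.2) concerns CDR and PPV "in the subgroup of patients who have negative baseline conventional imaging (classified at the site level". SAP 4.16.3.1 carries this through: "This will be a repeat of the primary efficacy using patients from the EAP with negative baseline conventional imaging (according to site reads". Protocol 3.2 and 5.2 define the same subgroup without naming a reader.

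**Truth for a PET-positive lesion without histology.** This comes from a different read. Under SAP 3.2.2.3, "Reads of the conventional and confirmatory imaging as SoT will be directed by rhPSMA-7.3" findings, for location only, and three central reviewers reach consensus. Lesions "will be categorized by the consensus central SoT read as positive, negative or indeterminate using all available conventional and confirmatory imaging". SAP 3.2 makes confirmation by any one of Steps 1 to 4 enough. Under Step 2 (SAP 3.2.2.1), where historical scans exist, "then these images can be used along with baseline to establish the SoT". If the local reader judges those scans sufficient, Steps 3 and 4 are not required. SAP Table 1 lets the panel accept subtle findings: sub-centimetre changes in node size, and "b) small bone CT scleroses to be indicative of cancer".

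**Upstaging.** Exploratory endpoint 3 (SAP 3.3.3) is framed against conventional imaging. SAP 4.16.4.3 restricts it to patients with a negative baseline scan and does not say whose read. The numerator takes any proof: "The patients will be counted if they have any TP lesion in either of the regions".

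**What is listed.** SAP 4.15 lists each blinded-reader lesion by histology, Step 2, or Steps 3 and 4. "In addition, a listing will be provided showing the modality of the reason".

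**The concern.** The same baseline scan is read twice for two purposes. The site read decides whether a man belongs to the negative group. The central read, knowing where PET was positive and free to accept small changes, may then use that scan to prove his PET lesion. No rule in 4.16.3.1 or 4.16.4.3 separates the man in whom this happens.

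The issue is what the results can be used to say. Protocol 2 explains that the study is meant to support PET early in the workup because conventional imaging is insensitive. The subgroup result and the upstaging count are the natural evidence that PET shows what conventional imaging does not. For that use, two kinds of True Positive need to be told apart: disease absent from the conventional scans, and disease the panel confirmed on them but the site did not call.

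**Working it through.** **1. Can it happen under the text?** Take a man with historical and baseline scans, no histology, and a baseline the site called negative.

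- He enters the subgroup on the site read (2.2, 4.16.3.1).
- All his conventional scans go to the panel; site-negative scans are not excluded (3.2.2.3).
- If the panel sees suspicious change across historical and baseline scans at the PET-positive site, the lesion is True Positive (3.2, 3.2.2, 3.2.2.1).
- He counts in the subgroup CDR, his region counts in the PPV, and he counts as upstaged if the site read also applies in 4.16.4.3.

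Nothing in the text interrupts this path.

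**2. The plan's own figures.** The documents give no planning figure for this subgroup. The stated powers reproduce with one-sided exact tests at 0.025. For PPV, with 190 cases, 62.5% against 73.5% and rejection at 133 or more, power is 87.9% (stated as above 88%). For CDR, with 316 patients, 36.5% against 49% and rejection at 133 or more, power is 99.4% (stated as above 99%). Neither uses the subgroup definition.

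**3. Illustration of size.** Let c be the rate under the current rule. Let q be the share of True Positives whose only proof is Step 2. The values of c are the overall planning values (SAP 4.18.1), standing in for the subgroup. The values of q are assumed, and the same q is used for men and regions only for simplicity.

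- Removed from numerator and denominator: c(1 − q) / (1 − cq)
- Kept but not credited: c(1 − q)

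At q = 20%:

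- CDR removed: 0.49 × 0.80 / (1 − 0.098) = 0.392 / 0.902 = 43.5%
- CDR not credited: 0.49 × 0.80 = 39.2%
- PPV removed: 0.735 × 0.80 / (1 − 0.147) = 0.588 / 0.853 = 68.9%

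| q (assumed) | CDR removed | CDR not credited | PPV removed |
|---|---|---|---|
| 0% | 49.0% | 49.0% | 73.5% |
| 10% | 46.4% | 44.1% | 71.4% |
| 20% | 43.5% | 39.2% | 68.9% |
| 30% | 40.2% | 34.3% | 66.0% |

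The number of upstaged men falls by the share q in either version. The two versions differ only if that number is expressed as a proportion of baseline-negative men.

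**4. Is the direction fixed?** For these two versions, yes, because only True Positives are touched. It is not fixed if every baseline scan were re-read centrally without PET direction, since a share s of the other men would then leave too. CDR becomes c(1 − q) / [c(1 − q) + (1 − c)(1 − s)]. With c = 49% and q = 10%:

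- s = 0: 0.441 / 0.951 = 46.4%
- s = 10%: 0.441 / 0.900 = 49.0%
- s = 20%: 0.441 / 0.849 = 51.9%

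**The case against.** The strongest reply is that the subgroup is defined by the site read. A lesion the local reader did not call and the truth standard confirms is a valid True Positive in that population. This stands. A reader might infer that the subgroup CDR and PPV are overstated as estimates; the documents do not support that. Indeterminate, unconfirmed and unverified lesions all count as False Positive (SAP 3.2.2.3, 4.16.1.2.1), which pulls both rates down, so the net direction against the truth is not settled.

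Four further points limit the concern:

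- Imaging truth is longitudinal (SAP 3.2.2), and Table 1 places its examples under longitudinal assessment. Change on a later scan from a truly negative baseline is legitimate proof. The objective criteria sit in the Independent Review Charter, which is not among the documents, so whether a lone baseline finding could suffice cannot be determined.
- Step 2 waives follow-up imaging only if the local reader finds the scans sufficient, and inconclusive cases go on to confirmatory imaging (SAP 3.2.2.2, 4.12.3). With histology preferred, this steers many site-negative men to Steps 1, 3 or 4. It lowers the likely share without excluding Step-2-only proof.
- Section 4.16.4.3 names no reader, so the site read is an inference there.
- The 4.15 listings would let a reader work out the share by hand.

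The planned split by histology (SAP 4.16.3.2) does not answer the point: it pools Step 2 with Steps 3 and 4 and is not crossed with baseline-negative status.

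Scoring Step-2-only regions as unconfirmed in the PPV would be the wrong remedy. It would turn panel-confirmed disease into False Positives and, at an assumed 20%, give 0.735 × 0.80 = 58.8% against 68.9% on removal.

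**Conclusion.** The point holds as a limit on interpretation. CDR and PPV in site-negative men answer the question as the SAP defines it. They do not, as planned, show how much disease PET finds that conventional imaging does not show. The upstaging count has the same limit, provided the site read applies there.

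The size is unknown, because neither the subgroup size nor the Step-2-only share is given. Across assumed shares of 10% to 30% at the planning values, removal lowers CDR by about 3 to 9 points (49.0% to between 46.4% and 40.2%) and PPV by about 2 to 7.5 points (73.5% to between 71.4% and 66.0%). These figures show sensitivity; they do not estimate bias.

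A reader might also infer that the primary result is affected. It is not: the subgroup definition does not enter the primary endpoints, the power or the success rule, and these analyses are descriptive (Protocol 16.5).

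**What to change.** 1. In SAP 4.16.4.3, state which read defines a negative baseline scan.
2. In SAP 4.16.3.1 and 4.16.4.3, use the step and reason already listed under 4.15 to give, for each reader and the majority, the number of True Positives proven by Step 1, by Step 2 only, and by Steps 3 and 4. Define Step 2 only as no confirming histology and panel reasons citing only historical and baseline scans. A man or region with any True Positive lesion proven another way stays as planned.
3. Add a descriptive sensitivity analysis repeating CDR, PPV and the upstaging count with men or regions whose only proof is Step 2 removed. Give a not-credited version for CDR and upstaging, but not for PPV.
4. Group by truth step and not by whether a scan followed PET, because baseline scans may be taken up to 2 weeks after PET (SAP 4.2, 4.12.1).
5. Do not call the two results upper and lower bounds. The False Positive defaults act on both, and Steps 3 and 4 may still use the baseline scan as comparator.

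The cost is SAP wording and a few table rows from data already planned for listing, plus a second figure that can only be equal or less favourable.
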